5.2.2 Janssen Ad26.CoV2.S Vaccine Dosing

There are no required medications pre or post vaccination with the Janssen Ad26.COV2.s vaccine. Dosage of study drug is defined as such:

- A single 0.5 mL dosage administered via an intramuscular injection. Typical administration time is less than a minute.

For Segment I, vaccination with the Janssen Ad26.COV2.s vaccine will occur 2 weeks post randomization in the no change in immunosuppression medication group (see Schedule of Events 2B). For those who will have an adjustment to their immunosuppression medication (see Schedule of Events 2C) vaccination with the Janssen Ad26.COV2.s vaccine will be 2 weeks after medication adjustment.

In Segment II, vaccination with the Janssen Ad26.COV2.s vaccine will occur three weeks after the result from the anti-SARS-CoV-2 spike protein test results which will be obtained on Day 28 of Segment I. On Day 42 the subject will begin immunosuppressive adjustment and the 2nd vaccination will be on Day 56.

There is no treatment for the Initial Responder group.

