3.1.2 Segment II

In Segment I, 250 subjects will receive the Janssen Ad26.CoV2.S vaccine without immunosuppression adjustment (i.e. they will be maintained on their current immunosuppression). We expect that adjusting immunosuppression increases the response to the Janssen Ad26.CoV2.S vaccine compared to no adjustment. Thus, it is possible that patients from Segment I who were maintained on current immunosuppression, but did respond to receiving the Janssen Ad26.CoV2.S vaccine (i.e. they failed to reach the SARS-CoV-2 spike protein antibody cutoff (≥ 250 U/mL) at 28 days might respond if they underwent immunosuppression adjustment and receive a 2nd vaccination of using the Janssen Ad26.CoV2.S vaccine. A 2nd dose of the Janssen Ad26.CoV2.S vaccine will be offered to these patients. The approach will be similar to Segment I, in that the dose of the Janssen Ad26.CoV2.S vaccine will occur at 2 weeks after immunosuppression adjustment.

The number of patients in this segment could be anywhere between 0 and 250. There is no data to provide an estimate of enrollment, as it can be affected many factors. In prior studies of the mRNA vaccine, most of the low responders developed high levels of antibody after revaccination. If 50% of the non-responders are included here (n=75) and 25 low responders, then the number of subjects receiving the Janssen Ad26.COV2.S vaccine in Segment II would be 100.

Clinical follow-up will be for two years after receiving the Janssen Ad26.CoV2.S vaccine and analysis will focus on transplant specific outcomes (graft and patient survival, rejection episodes, etc.), general health outcomes (incidence of new diagnoses) and COVID specific outcomes (incidence of *de novo* SARS-CoV2 infection and clinical course/outcome).

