4.5 Criteria for Temporarily Delaying Administration of Study Vaccination

The following events constitute a temporary contraindication to study vaccination:

- Clinically significant acute illness at the time of vaccination. This does not include minor illnesses, such as diarrhea or mild upper respiratory tract infection.
- Fever (body temperature $\geq 38.0^{\circ}\text{C}/100.4^{\circ}\text{F}$) within 24 hours prior to the planned time of vaccination.
- An illness which in the judgement of the sponsor-investigator may interfere with reactogenicity.
- Additional adjustment needed to immunosuppression medication.

If any of these events occur at the scheduled time for receiving the first dose of the Janssen Ad26.CoV2.S vaccine, randomization at a later date within the screening window is permitted at the discretion of the sponsor-investigator.

If randomization cannot occur within the screening window, the COVID spike protein test will be repeated. If any of these events occur at the scheduled time for the second vaccination, the vaccination can be rescheduled, as long as this is in agreement with the allowed windows (see Visit Windows in the Schedules of Activities).

If the second vaccination visit cannot be rescheduled within the allowed window or the contraindications to vaccination persist, the sponsor-investigator should be contacted for further guidance.

For randomized participants who could not be administered with the Janssen Ad26.COV2.S vaccine on the day of randomization for any reason, vaccination can be administered on another day provided that vaccination occurs within the 28-day screening visit window. Baseline visit procedures should be performed prior to vaccination and within the visit window. The following study visits and procedures will be adjusted accordingly.

Participants who cannot be dosed within the 28-day screening window should be discontinued from the study and should not be rescreened.

5 Study Drug

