5.2 Treatment Regimen

5.2.1 Immunosuppression Adjustment

Immunosuppression adjustment will occur 2 weeks prior to receiving the Janssen Ad26.COV2.S vaccine and continue for 28 days receiving the Janssen Ad26.COV2.S vaccine.

Given that transplant patients are maintained on immunosuppressive regimens that vary slightly, immunosuppression adjustment will need to be somewhat individualized to the patient. However, general rules can be implemented.

Two weeks prior to receiving the Janssen Ad26.COV2.S vaccine, patients randomized to immunosuppression adjustment (or offered immunosuppression adjustment in Segment II) will be considered individually and adjustments will be made by a nephrologist with knowledge of the patient's clinical situation. General rules for adjustment are as follows:

1. For patients receiving mycophenolate mofetil (MMF) or azathioprine (AZA), a calcineurin inhibitor (CNI) (typically tacrolimus or cyclosporine), and Prednisone. Adjustment will involve stopping MMF or AZA and starting 10 mg Prednisone/day. **Note:** most patients will be in this group.
2. For patients not on MMF, but on CNI and Prednisone, the CNI dose will be decreased by 50%,
3. For patients on belatacept, which is typically taken with MMF and Prednisone, MMF will be stopped, and belatacept and Prednisone will be modified to 10 mg a day.
4. Other patients are adjusted on a case-by-case basis by the sponsor-investigator and the co-investigators—ex. Tac-mTOR inhibitor—Reduce Tac by 50%.

28 days after receiving the Janssen Ad26.COV2.S vaccine, study subjects in this arm will resume their prior doses of immunosuppression and will be followed as per protocol and as clinically indicated by the transplant team.

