Visit Description	Screening visit		Janssen Ad26.COV2.S vaccine	Follow up						Safety		
Visit Window	-30 / +7 Days	+/- 3 days	-4/+1 day	+/- 1 Day	+/- 2 Day	+/- 7 Day	+/- 7 Days	+/- 15 Days	+/- 30 Days	+/- 60 Days	+/- 60 Days	N/A

Safety assessment AFTER vaccination

Subject Symptom Report ^b			Continuous									
Diary compliance phone call				X								
Safety follow-up phone call ^c					X							
Symptom Directed Exam as needed						X	X	X	X			X
Safety Follow Up Questionnaires ^d			X	X	X	X			X	X	X	
COVID-19 Surveillance and Evaluation ^e	X	X ^f	X			X	X	X	X	X	X	X
Patient and Graft Status	X	X	X			X	X	X	X	X	X	X
MAAE Monitoring ^g				Continuous								
(S)AE Monitoring ^h				Continuous								

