Visit Description	Screening visit		Janssen Ad26.COV2.S vaccine						Follow up			Safety
Visit Window	-30 / +7 Days	+/- 3 days	-4/+1 day	+/- 1 Day	+/- 2 Day	+/- 7 Day	+/- 7 Days	+/- 15 Days	+/- 30 Days	+/- 60 Days	+/- 60 Days	N/A

o Tacrolimus, Cyclosporine and MMF serum drug levels in subjects who are receiving these drugs or who were receiving these drugs at the time of enrollment.

p Patient will be provided a dairy to record symptoms from post-vaccination through day 7. If any solicited signs and symptoms reported in the diary are not resolved by the Day 7 contact, the subject will continue to record their daily symptoms in the diary until the Day 28 Visit or until they are resolved, whichever comes first. A thermometer will be provided for daily temperature check.

q A study investigator will be notified if the subject reports symptoms that require further medical review and follow-up as necessary. An Unscheduled Visit conducted by a study investigator will be conducted if needed

r Obtain anti-SARS-CoV-2 spike protein antibody and anti- anti-SARS-CoV-2 Nucleocapsid antibody levels if previous levels at Day 180 post vaccination were detectable.

Schedule of Events 3: Segment II^a

Study Event	Day 28 (Segment I)	Day 42	Day 56	Day 59	Day 63	Day 70	Day 84	Day 146	Day 236	1 Year	2 Years	Unscheduled Visit ^b
Days post 2nd Janssen Ad26.COv2.s vaccine			0	3	7	14	28	90	180	365	730	Safety
Visit Window	+/- 7 Days	+/- 7 Days	-4/+1 day	+/- 1 Day	+/- 2 Day	+/- 7 Day	+/- 7 Days	+/- 15 Days	+/- 30 Days	+/- 60 Days	+/- 60 Days	N/A
Prior & Concomitant Medications & Therapies	X		X			X	X	X	X			X
Immunosuppression Medications		X	X			X	X	X	X	X	X	X
Nephrology Consult			X									
Complete Physical Exam				X								
CBC with Diff (Platelet Count) ^c			X				X					
Tacrolimus, cyclosporine and/or MMF Drug Levels ^m				X								
Vital Signs ^d				X								X
Serum Pregnancy Test ^e				X								
Janssen Ad26.CoV2.S Dosing			X									
Risk Factor Assessment and Kidney Transplant Follow Up Questionnaire				X							X	
Immunosuppression Adjustment		X						X ^f				
Anti-SARS-CoV-2 spike protein	X		X			X	X	X	X	X ^p		
Anti-SARS-CoV-2 Nucleocapsid Total Antibody Test	X		X			X	X	X	X	X ^p		
Safety assessment DURING vaccination												
Pre and Post Vaccination Symptoms (questionnaire)			X									
Post-Vaccine Observations ^g			X									
Safety assessment AFTER vaccination												
Subject Symptom Report ⁿ				Continuous								
Diary compliance phone call				X								

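### Schedule 3's ±7-day window on the Segment II immunosuppression adjustment permits a lead of 3 to 22 days to the second dose (7 to 21 if counted from the actual dose), against a stated 2 weeks

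*Combined protocol and SAP*

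**What the plan says.** The text gives one interval throughout. Section 3.1.2, on Segment II, says that "the dose of the Janssen Ad26.CoV2.S vaccine will occur at 2 weeks after immunosuppression adjustment". Section 5.2.1 places the change two weeks before vaccination and covers both segments: "patients randomized to immunosuppression adjustment (or offered immunosuppression adjustment in Segment II) will be considered individually". Section 5.2.2 fixes the days: "On Day 42 the subject will begin immunosuppressive adjustment and the 2nd vaccination will be on Day 56". None of these gives a tolerance.

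The schedules in Section 6.6 give tolerances, and they differ by segment. The window row of Schedule 3 (Segment II) begins, for Days 28, 42 and 56: "Visit Window +/- 7 Days +/- 7 Days -4/+1 day". The row of Schedule 2C (Segment I, adjusted arm) begins, for Days -21, -14 and 0: "Visit Window -30 / +7 Days +/- 3 days -4/+1 day". Footnote e of Schedule 2C repeats that the reduction happens 14 days ahead of the Day 0 vaccination. Schedule 3 has no such footnote.

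Section 6.2 says Segment II procedures follow the manner and timetable of Segment I, and refers to Schedule 3 for detail. Section 4.5 says that if the second dose has to be delayed, "the vaccination can be rescheduled, as long as this is in agreement with the allowed windows"; failing that, "the sponsor-investigator should be contacted for further guidance". It does not mention the interval since adjustment.

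**The concern.** Secondary objective 1 is the response to a second dose given with immunosuppression adjusted. The two weeks on the adjusted regimen before the dose are part of what defines that intervention. A site working from Schedule 3 could start the adjustment a few days before the dose, or about three weeks before it, and record no deviation. Patients with quite different preparation would then be pooled in one response rate.

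The same step is held more tightly in Segment I, and the protocol describes the two segments as alike in approach (Section 3.1.2) and in schedule (Section 6.2). No reason is given for the looser window. The only rule on moving the second dose (Section 4.5) refers to the windows, so a site cannot tell from the documents whether the 2-week statement or the window governs.

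**Working it through.** **Inputs.** Segment II: adjustment Day 42 ±7, so Days 35 to 49; dose Day 56 -4/+1, so Days 52 to 57 (Schedule 3). Segment I: adjustment Day -14 ±3, so Days -17 to -11; dose Day 0 -4/+1, so Days -4 to 1 (Sections 6.1.2 and 6.1.3, Schedule 2C).

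**The plan's own figure.** 56 - 42 = 14 days, which agrees with the stated 2 weeks.

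**Windows applied independently.** Minimum lead = earliest dose - latest adjustment. Maximum lead = latest dose - earliest adjustment.
- Segment II: 52 - 49 = 3; 57 - 35 = 22.
- Segment I: -4 - (-11) = 7; 1 - (-17) = 18.

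**Adjustment window counted from the actual dose.** Lead = 14 ± window.
- Segment II: 14 - 7 = 7; 14 + 7 = 21.
- Segment I: 14 - 3 = 11; 14 + 3 = 17.

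| Reading | Segment II | Segment I |
|---|---|---|
| Stated in text | 14 | 14 |
| Windows independent | 3 to 22 | 7 to 18 |
| Counted from actual dose | 7 to 21 | 11 to 17 |

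**Can both rules be met?** Allow the 2-week rule a ±3-day tolerance, that is 11 to 17 days. A Segment II adjustment on Day 35 can be followed by a dose on Day 52 (17 days), and one on Day 46 by a dose on Day 57 (11 days). An adjustment on Day 47, 48 or 49 is in window, but a dose by Day 57 gives at most 10, 9 or 8 days. So on 3 of the 15 permitted adjustment days, no in-window dose comes within three days of the stated lead. In Segment I every permitted adjustment day leaves such a dose: Day -11 allows up to 1 - (-11) = 12 days, and Day -17 allows -4 - (-17) = 13.

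**Effect of a ±3 window in Segment II.** Adjustment Days 39 to 45: minimum 52 - 45 = 7, maximum 57 - 39 = 18. This equals Segment I.

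**The case against.** The best defence is that the text already settles the matter. Sections 3.1.2, 5.2.1 and 5.2.2 all give two weeks, Section 6.2 points Segment II to Segment I's schedule, and Schedule 2C states 14 days inside a schedule. A sensible site would plan for 14 days and treat the window as slack for the contact. The 3-to-22-day range also needs both windows at opposite extremes. Because Schedule 3 numbers visits after the second dose from that dose, the adjustment window might be meant to count from it too, which gives 7 to 21 days.

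Much of this stands. Two weeks is plainly the intention, 3 to 22 is the outer limit, and Segment I is not exact either, so the difference is one of degree. But no passage gives the text precedence, the numbering row in Schedule 3 leaves Day 42 blank, and Section 6.2 itself defers to Schedule 3. Even on the narrower reading, Segment II stays wider than Segment I.

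It is also fair that immunosuppression medication is recorded at Days 42 and 56, so the actual lead should be recoverable, and that Section 6.8 plans regression on factors related to response. That helps interpretation afterwards; it does not make the regimen uniform.

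**Conclusion.** The discrepancy holds as a minor point. Schedule 3 permits a lead of 3 to 22 days if the windows are independent, or 7 to 21 days if the adjustment is timed from the actual dose, against a stated 14. Segment I permits 7 to 18, or 11 to 17. The documents neither explain the difference nor say which rule prevails. These are limits of what is permitted; how many patients would fall near them is unknown, and Section 3.1.2 puts Segment II anywhere between 0 and 250 patients.

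Three stronger readings are not supported.
- A reader might infer that total time on adjusted therapy runs from 31 to 50 days, by adding 28 to the lead. That applies the windows to the start but the fixed text to the end ("28 days after receiving the Janssen Ad26.COV2.S vaccine, study subjects in this arm will resume their prior doses of immunosuppression"), although the 28-day visit has its own ±7-day window. If the text governs, the total is 14 + 28 = 42 days.
- A reader might infer a bias in the response rate or a rejection hazard. The documents do not show how response depends on lead time, so size and direction are unknown. Section 1.5.9 reports that reductions in practice usually last much longer than 6 weeks, with clinical rejection below 10%.
- A reader might take the Section 5.2.2 clause that times the dose three weeks after the antibody result as a second conflict, since 28 + 21 = 49. A result available around Day 35 (turnaround assumed) gives 35 + 21 = 56, so the clause need not conflict.

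The endpoint affected is secondary, non-randomized and has no power calculation. The randomized primary comparison uses Segment I only, so its power and alpha are unchanged.

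**What to change.** In Schedule 3, change the Day 42 window from ±7 to ±3 days (Days 39 to 45), and add the Schedule 2C footnote so that adjustment is placed 14 days before the actual second dose. The window change alone raises the minimum lead from 3 to 7 days and lowers the maximum from 22 to 18. The footnote tells sites what to aim for.

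If the sponsor prefers to keep late starters, an alternative is to define adjustment as 14 ±3 days before the actual dose and let Section 4.5 allow a dose up to Day 63. Adjustments on Days 47 to 49 would then be dosed from Days 58 to 60 (11-day lead) or on Days 61 to 63 (14-day lead). Affected doses fall on Days 58 to 63, and their 28-day visits on Days 86 (58 + 28) to 91 (63 + 28), inside the present Day 84 ±7 window. The bar on pre-exposure prophylaxis in Section 5.6 ends with that visit, so it would not run past a date the window already allows.

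The first option costs one schedule cell and one footnote; the second also needs a sentence in Section 4.5. The practical downside of the preferred change is less flexibility in scheduling the adjustment.

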5.3 Method for Assigning Subjects to Treatment Groups

Subjects will be placed in each group by their anti-SARS-CoV-2 spike protein antibody results obtained between screening and baseline:

Segment I

- Anti-SARS-CoV-2 spike protein antibody level >250 U/ml—no vaccination with the Janssen Ad26.CoV2.S vaccine, 2 year observation only
- Anti-SARS-CoV-2 spike protein antibody level >0, but <250 U/ml—vaccination with the Janssen Ad26.CoV2.S vaccine. If antibody levels remain <250 U/ml subjects will move to Segment II.
- Anti-SARS-CoV-2 spike protein antibody levels 0 U/ml—randomized to vaccination with the Janssen Ad26.CoV2.S vaccine with 1) no change in immunosuppression or 2) immunosuppression adjustment. For subjects that did not have a change in immunosuppression, if antibody levels remain <250 U/ml subjects will move to Segment II.

Segment II

- Study subjects from Segment I who received Janssen Ad26.CoV2.S without immunosuppression adjustment and their anti-SARS-CoV-2 spike protein antibody levels remain <250 U/ml, will be offered a second dose of the Janssen Ad26.CoV2.S vaccine with immunosuppression adjustment this time.

5.4 Preparation and Administration of Study Drug

The Janssen Ad26.CoV2.S vaccine is supplied in a carton of 10 single-dose vials out of which one dose of 0.5 mL will be withdrawn from administration.

Refer to the IPPI for additional guidance on study vaccine administration.

Please refer to IPPI/IFU included in the Quality Agreement containing clear instructions on shipping, preparation and storage.

- Confirm that the Janssen Ad26.CoV2.S vaccine is a colorless to slightly yellow, clear to very opalescent sterile suspension that does not contain a preservative.
- Visually inspect the Janssen Ad26.CoV2.S vaccine vials for particulate matter and discoloration prior to administration. If either of these conditions exist, the vaccine will not be administered.
- Before withdrawing each dose of vaccine, carefully mix the contents of the single-dose vial by swirling gently in an upright position for 10 seconds. Do not shake.
- Each dose is 0.5 mL. Each vial contains 1 dose. Do not pool excess vaccine from multiple vials.

The Janssen Ad26.CoV2.S vaccine will be administered by a vaccine administrator in the clinical setting. For the purposes of this protocol, a vaccine administrator will be defined as a qualified nurse, medical doctor, or otherwise qualified healthcare professional. The following administration guidelines will be followed:

- The administrator will visually inspect each dose in the dosing syringe prior to administration to:
 - Verify the final dosing volume of 0.5 mL
 - Determine if the vaccine is discolored or contains particulate matter. In this situation the vaccine would not be administered.
- 2. Janssen Ad26.CoV2.S vaccine will be injected intramuscularly into the deltoid muscle, preferably of the non-dominant arm. If an injection cannot be given in the deltoids due to a medical or other contraindication (for example, tattooed upper arms rendering it difficult to assess site reactogenicity), use alternative locations such as the hip, thigh or buttocks (to be avoided in overweight participants). In all circumstances, IM injections in other locations than the upper arm are not considered protocol deviations.

Currently there is no information on the co-administration of the Janssen COVID-19 vaccine with other vaccines.

5.5 Subject Compliance Monitoring

Study vaccines will be administered intramuscularly by a study vaccine administrator. The date and time of each study vaccine administration and the location used will be recorded in the eCRF. Subjects will not be allowed to administer the vaccine to themselves or others. Study subjects found

to be significantly non-compliant with study procedures will not be offered to receive the Janssen Ad26.COv2.s vaccine.

5.6 Prior and Concomitant Therapy

Information about the subject's past Pfizer-BioNTech (BNT162b2 vaccine) or Moderna (mRNA-1273) vaccine history will be recorded at Screening.

All pre-study therapies (excluding vitamins, herbal supplements; non-pharmacologic therapies such as electrical stimulation, acupuncture, special diets, and exercise regimens) administered up to 30 days before the 1st vaccination with the Janssen Ad26.CoV2.S vaccine must be recorded at baseline.

For all participants, concomitant therapies associated with an SAE, or suspected AESI meeting the criteria outlined in Section 8.2, will be collected and recorded in the eCRF from the moment of 1st vaccination with the Janssen Ad26.CoV2.S vaccine through the end of the study. Concomitant therapies associated with MAAEs will be collected and recorded in the eCRF from the moment of 1st vaccination until 6 months after the last vaccination. Concomitant therapies associated with MAAEs leading to study discontinuation will be recorded in the eCRF during the entire study.

For all participants, concomitant therapies associated with COVID-19 will be captured in the electronic eCRF for the duration of the study.

Concomitant therapies associated with AEs will be collected and recorded in the eCRF from the time of 1st vaccination through 28 days after the last vaccination. If the signs and symptoms are not resolved by 28 days post-vaccination, the concomitant therapies associated with these AEs will be collected by the participants and recorded in the eCRF until they are resolved, or the participant exits the study.

Antipyretics are recommended post-vaccination for symptom relief as needed. Prophylactic antipyretic use is not encouraged; however, in some instances, it could be considered for participants with special circumstances and/or comorbidities.

Participants may not have received an investigational drug within 30 days (including investigational drugs for prophylaxis of COVID-19) or used an invasive investigational medical device within 30 days or received investigational Ig or investigational monoclonal antibodies within 3 months, or received convalescent serum for COVID-19 treatment within 4 months or received an investigational vaccine (including investigational Adenoviral-vectored vaccines) within 6 months before the planned administration of the 1st dose of the Janssen Ad26.CoV2.S vaccine. During the study, the use of investigational vaccines, drugs or devices is not allowed. Treatment with investigational COVID-19 drugs after diagnosis of a COVID-19 case is allowed during the follow-up period and needs to be recorded in the COVID-19 episode description.

Licensed live attenuated vaccines should be given at least 28 days before or at least 28 days after a study vaccination. Other licensed (not live) vaccines (e.g., influenza, tetanus, hepatitis A, hepatitis B, rabies) should be given more than 14 days before (or more than 14 days after, as per Exclusion

Criteria) administration of any dose of the Janssen Ad26.CoV2.S vaccine in order to avoid potential confusion of adverse reactions and potential immune interference. If a vaccine is indicated in a postexposure setting (e.g., rabies or tetanus), it must take priority over the Janssen Ad26.CoV2.S vaccine. Receipt of any COVID-19 vaccine (outside the study) at any timepoint during the study must be recorded. The name and date(s) of administration of the COVID-19 vaccine should be recorded in the eCRF.

Subjects should not receive any pre-exposure prophylactic medications for COVID-19 until after completion of the Day 28 Visit for subjects in Segment I or the Day 84 Visit for subjects in Segment II. If pre-exposure prophylactic medication for COVID-19 is administered prior to these visits the investigator should contact the sponsor-investigator to discuss if the subject should be discontinued from the study.

The sponsor-investigator must be notified in advance (or as soon as possible thereafter) of any instances in which prohibited therapies are administered. The participant should remain in the study but receive no further study vaccination.

